18.7. OTHER SAFETY ASSESSMENTS

18.7.1. COLUMBIA SUICIDE SEVERITY RATING SCALE (C-SSRS)

C-SSRS score observed at any post-baseline assessment will be summarized using descriptive statistics for categories of Suicidal Ideation, Suicidal Behavior, as well as for the individual questions associated with each category. Treatment-emergence of suicidal ideation and suicidal behavior during OLE will also be summarized. Responses for each of the 12 corresponding questions will also be listed.

18.7.2. ANTI-DRUG ANTIBODIES TO GANTENERUMAB

Frequencies and percent of Anti-Drug Antibodies (ADA) to Gantenerumab will be summarized for evaluable subjects at baseline prior to first gantenerumab exposure (in either double-blind or open-label period) by positive/negative status and post baseline by the following categories:

- Treatment-emergent ADAs
 - Treatment-induced ADAs- defined as a subject with a negative or missing baseline ADA result and at least one positive post-baseline ADA result.

Author: [REDACTED]

Version Number:

7

Version Date:

07Dec2023

Template No.: CS_TP_BS016 Revision 6

Reference: CS_WI_BS005

Effective Date: 02Dec2019

- Treatment-enhanced ADAs- defined as a subject with a positive ADA result at baseline who has one or more post-baseline titer results that are >2.5-fold greater than the baseline titer result.
- No treatment-emergent ADAs
 - Negative ADAs
 - Treatment Unaffected ADAs- defined as a subject with a positive ADA result at baseline and where all post-baseline titer results are less than or equal to the baseline result.

All ADA results will be listed by subject, visit, specimen type and parameter. For subjects with a treatment emergent positive ADA, all adverse events will be listed with along with results from the most recent ADA and the most recent positive ADA.

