18.4. LABORATORY EVALUATIONS

Results from the central laboratory will be included in the reporting of this study for hematology, chemistry and urinalysis. Presentation of results for drug-specific laboratory parameters including gantenerumab levels and anti-gantenerumab antibodies are described in [Section 18.7.2](#). A list of expected laboratory assessment visits can be found in the protocol Appendix 3, Section 3.2. [Table C](#) identifies the laboratory parameters and order of parameters to be included in table summaries.

Author:	[REDACTED]	Version Number:	7
	[REDACTED]	Version Date:	07Dec2023
Template No.:	CS_TP_BS016 Revision 6	Reference:	CS_WI_BS005
Effective Date:	02Dec2019		

Copyright © 2009, 2010, 2012, 2016, 2018, 2019 [REDACTED] All rights reserved. The contents of this document are confidential and proprietary to [REDACTED] Holdings Inc. and its subsidiaries. Unauthorized use, disclosure or reproduction is strictly prohibited.

Table C: Laboratory Parameters

Chemistry	Hematology	Urinalysis
ALT (SGPT)	Basophils	Bilirubin
AST (SGOT)	Basophils %	Blood
Albumin-QT	Eosinophils	Clarity
Alkaline Phosphatase-QT	Eosinophils %	Color
Calcium (EDTA)	Hematocrit	Glucose
Cholesterol (High Performance)	Hemoglobin	Ketones
Creat Cir, Cockcroft & Gault	Lymphocytes	Leukocyte Esterase
Creatinine Kinase	Lymphocytes (%)	Nitrate
Creatinine (Rate Blanked)	MCH	Protein
Direct Bilirubin	MCHC	Specific Gravity
GGT	MCV	Urobilinogen
LDH	Monocytes	pH
Magnesium	Monocytes (%)	
Phosphorus	Neutrophils	
Serum Chloride	Neutrophils (%)	

Author: [REDACTED]

Version Number:

7

Version Date:

07Dec2023

Template No.: CS_TP_BS016 Revision 6

Reference: CS_WI_BS005

Effective Date: 02Dec2019

Chemistry	Hematology	Urinalysis
Serum Glucose	Platelets	
Serum Potassium	RBC	
Serum Sodium	WBC	
Serum Uric Acid		
Total Bilirubin		
Total Protein		
Triglycerides		
Urea Nitrogen		

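### The ADA sub-rows under *No treatment-emergent ADAs* do not cover baseline-positive participants whose titer rises by no more than 2.5-fold

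*SAP*

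**What the plan says.** SAP Section 18.4 sends the reader elsewhere for ADA output ("Presentation of results for drug-specific laboratory parameters including gantenerumab levels and anti-gantenerumab antibodies are described in" Section 18.7.2), and that section holds the only readable ADA classification in either document. It summarises evaluable participants at baseline "by positive/negative status and post baseline by the following categories". The post-baseline categories are:

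- Treatment-emergent, *Treatment-induced*: "a subject with a negative or missing baseline ADA result and at least one positive post-baseline ADA result".
- Treatment-emergent, *Treatment-enhanced*: positive at baseline, and the participant "has one or more post-baseline titer results that are >2.5-fold greater than the baseline titer result".
- Not treatment-emergent, "Negative ADAs": listed without a definition.
- Not treatment-emergent, *Treatment Unaffected*: positive at baseline, "where all post-baseline titer results are less than or equal to the baseline result".

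There is no residual category. The section also provides for a listing of all ADA results by participant, and for a listing of adverse events in participants with a treatment-emergent positive ADA.

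**The concern.** The two definitions for baseline-positive participants use different cut-points. *Treatment-enhanced* begins above 2.5-fold, which implies that a smaller rise is not regarded as enhancement. *Treatment Unaffected* ends at 1-fold and allows no rise at all. Between them lies a band of titers with no definition.

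At stake is a table whose rows can be reconciled. Followed literally, the rules leave a participant in the band out of both sub-rows open to baseline-positive participants. A programmer must then leave that person uncounted or place them by a rule that the SAP does not contain, possibly after seeing the data.

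**Working it through.** The plan states no figure to reproduce. The check is whether the written categories cover every participant who has a post-baseline result.

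**Inputs** (all from SAP Section 18.7.2): baseline status (negative, missing or positive) and, for baseline-positive participants, R = highest post-baseline titer ÷ baseline titer. A negative post-baseline result is taken as R = 0.

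**Rules for baseline-positive participants**

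- *Treatment-enhanced*: at least one titer more than 2.5-fold, so R > 2.5.
- *Treatment Unaffected*: every titer at or below baseline, so R ≤ 1.
- *Treatment-induced*: closed to them, since it needs a negative or missing baseline.
- *Negative ADAs*: undefined, but by its name it cannot hold a baseline-positive participant whose titer rose.

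**Result**

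| R | Category met |
|---|---|
| 0, 0.5, 1.0 | Treatment Unaffected |
| 1.01, 1.5, 2.0, 2.5 | none |
| 2.51, 3, 3.5, 4 | Treatment-enhanced |

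The uncovered band is 1 < R ≤ 2.5.

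**Sensitivity to wording.** The threshold is phrased as "post-baseline titer results that are >2.5-fold greater than the baseline titer result". Read as an increase of more than 2.5 times the baseline value, it becomes R > 1 + 2.5 = 3.5, and the band widens to 1 < R ≤ 3.5. The ordinary reading, R > 2.5, is used here.

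**Baseline-negative or missing.** Any positive post-baseline result gives *Treatment-induced*. Otherwise the participant is taken to be in *Negative ADAs*, an assumption because the SAP does not define that row. No gap arises here.

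**Effect on the outputs**

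- Treatment-emergent numerator: induced plus enhanced. A participant in the band fails both, so the count is unchanged.
- Denominator: evaluable participants, which does not depend on the sub-row.
- Adverse event listing: triggered by treatment-emergent status, so unchanged.
- *Treatment Unaffected*: short by the number of participants in the band.
- *Negative* + *Unaffected*: short of the full not-treatment-emergent count by the same number.

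**Size.** The documents give neither the baseline ADA prevalence nor the dilution scheme, so the number cannot be computed. If titers were reported in two-fold steps (an assumption), a one-step rise gives R = 2 and falls in the band. If each step exceeded 2.5-fold (also an assumption), no ratio could fall in it. For scale, Protocol Appendix 3 Section 4.1.2 gives an OLE recruitment goal of 60 to 90. If all were evaluable, one participant would be 1/90 = 1.1% to 1/60 = 1.7% of the denominator.

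**After the change.** With *Treatment Unaffected* set to R ≤ 2.5 and *Treatment-enhanced* to R > 2.5, every baseline-positive participant with a post-baseline result meets exactly one of the two definitions.

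**The case against.** The best defence is that little depends on this. The table is descriptive. SAP Section 18 plans no statistical comparison of safety data unless one is specified, and none is specified for ADA. Every ADA result is listed by participant, so nobody is hidden. The OLE ended early, the study report is to be abbreviated, and SAP Section 6 lets deviations be documented there. The band may also be empty. All of this stands, and it is why the point is minor.

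A reader might infer more: that these participants appear in no row at all, or that ADA incidence is left undefined. The documents support neither. The participants are counted in the baseline-positive row, and they clearly fail both treatment-emergent definitions, so they belong under the *No treatment-emergent ADAs* heading. Only their sub-row is missing. Nor can it be said that the table fails to add up at heading level: if that heading carries its own count as the complement of treatment-emergent, the two headings together do account for everyone. SAP Section 8 leaves such layout to templates that are not among the documents. Protocol Appendix 3 Section 1.12, on drug-specific tests, is partly redacted, so nothing is inferred from its silence.

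It is also fair to say that a separate row for small rises would close the gap as well. What the objection does not do is supply a rule for the band.

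**Conclusion.** The point holds as a minor defect in the definitions. The sub-rows under *No treatment-emergent ADAs* are not exhaustive: a baseline-positive participant with 1 < R ≤ 2.5 is not enhanced and also fails the *Treatment Unaffected* definition. This is a stated rule that misclassifies, not just a missing detail, because applying it literally undercounts *Treatment Unaffected*.

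The error goes no further than that row and the reconciliation of the sub-rows. No hypothesis test or efficacy result depends on it.

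The conclusion rests on the ordinary reading of the 2.5-fold threshold; the literal alternative only widens the band. It also rests on there being no further ADA rule in the templates or the redacted text.

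**What to change.** Redefine *Treatment Unaffected* in SAP Section 18.7.2 as a positive baseline ADA result, with post-baseline results available, and no post-baseline titer more than 2.5-fold above the baseline titer. Use the same threshold expression in *Treatment-enhanced*, preferably as a ratio of post-baseline to baseline titer, so that the two definitions are exact complements and cannot be read differently.

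The cost is one phrase in the SAP and the matching line of table programming. No assay, visit, model or listing changes.

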19. DATA NOT SUMMARIZED OR PRESENTED

The other variables and/or domains not summarized or presented are:

- Comments
- Physical Examination
- Pregnancy Report
- Volumetric MRI, fluid biomarkers, PET scan data, clinical efficacy parameters, and cognitive efficacy parameters which are not included in [Section 16](#).

These domains and/or variables will not be summarized or presented, but will be available in the clinical study database, SDTM and/or ADaM datasets.

[REDACTED] [REDACTED]

Author: [REDACTED]

Version Number:

7

Version Date:

07Dec2023

Template No.: CS_TP_BS016 Revision 6

Reference: CS_WI_BS005

Effective Date: 02Dec2019

APPENDIX 1. PROGRAMMING CONVENTIONS FOR OUTPUTS

OUTPUT CONVENTIONS

1. ABBREVIATIONS

RTF Rich text file format

2. INTRODUCTION

This document applies to standards used for outputting tables, listings and figures. It is intended to provide specifications to guide the statistician or statistical programmer in setting up specifications for programming tables, listings and figures. These standards should be used in the absence of customer specific standards.

3. OUTPUT FILE NAMING CONVENTIONS

File names should only consist of uppercase letters, digits (0 to 9) and underscores. A period should only be used to indicate a separator between the file name and the extension. No spaces, other special characters or punctuation marks are permitted.

As far as possible, output files should be in RTF format, although .DOC files are also permitted.

The program, program log and output file name should reflect the type and number of the statistical output. If this is not possible, then the output name should be at least as descriptive as possible. A prefix can be used to distinguish between a Table, Listing and Figure document ('T' for table, 'L' for listing and 'F' for figure). If there is only 1 digit in the number of the table, listing or figure in the place where 2 digits are possible, a leading zero should be added in the file name to make sorting consistent with the sequence (e.g., T14_3_01_1.RTF).

Author: [REDACTED]

Version Number:

7

Version Date:

07Dec2023

Template No.: CS_TP_BS016 Revision 6

Reference: CS_WI_BS005

Effective Date: 02Dec2019

4. PAPER SIZE, ORIENTATION AND MARGINS

The size of paper will be Letter.

The page orientation will be landscape.

Margins should provide at least 1 inch (2.54 centimeters) of white space all around the page, regardless of the paper size.

The number of columns per page (linesize) should be 134 for Letter.

The number of rows per page (pagesize) should be 51 for Letter.

5. FONTS

The font type 'Courier New' should be used as a default for tables and listings, with a font size of 8. The font color should be black. No **bolding**, underlining, *italics* or subscripting should be permitted. Super-scripts should be avoided. Single spacing should be used for all text.

6. HEADER INFORMATION

Headers should be defined as follows:

- On the left side of the header, the following will represent the top three lines:
 - Washington University
 - Protocol DIAN-TU-001
 - Gantenerumab OLE, [delivery name as either Dry Run or Final]
- On the right side of the header, the following will represent the top two lines, with the third line being blank:
 - Confidential
 - Page X of Y (where Y is the total number of pages for the output)

Author: [REDACTED]

Version Number:

7

Version Date:

07Dec2023

Template No.: CS_TP_BS016 Revision 6

Reference: CS_WI_BS005

Effective Date: 02Dec2019

- The header values as shown above should be placed at the top of the page (same place on each page)
- A blank line should appear between the header and the output title.
- The output identification number and title should appear, centered, in the next set of rows.
- The output population should appear, centered, below title row(s). The population should be spelled out in full.
- The following row should be a continuous row of underscores ('_') (the number of underscores should equal the linesize).
- Mixed case should be used for titles.
- The output titles should be designed so that they are arranged consistently through all outputs. For example, content (e.g., Vital Signs) followed by metric (e.g., Change from Baseline) e.g., Vital Signs – Change from Baseline.
- Titles should not contain quotation marks or footnote references.
- The column headings should be underlined with a row of underscores ('_')
- Column headings spanning more than one column should be underlined and have underscores on either side of the title and should be centered.
- Column headings containing numbers should be centered.
- In general, the population count should appear in the column header in the form “(N=XXX)”.
- “Statistic” should be the column header over n, Mean, SE, n (%) etc.
- As a rule, all columns should have column headings.

Author: [REDACTED]

Version Number:

7

Version Date:

07Dec2023

Template No.: CS_TP_BS016 Revision 6

Reference: CS_WI_BS005

Effective Date: 02Dec2019

7. TABLE AND LISTING OUTPUT CONVENTIONS

General:

- The first row in the body of the table or listing should be blank.
- The left-hand column should start in column 1. No indenting or centering of the output should occur.
- Rounding should be done with the SAS function ROUND.
- Numbers in tables should be rounded, not truncated.
- Alphanumeric output should be left aligned.
- Numbers should be decimal point aligned.
- Whole numbers should be right aligned.
- Text values should be left aligned.
- The first letter of a text entry should be capitalized.
- Listings of adverse events, concomitant medications, injection site reactions etc. should be sorted in chronological order, with earliest event or medication coming first.
- The treatment column order should be Placebo, Solanezumab, Gantenerumab, Total, with all columns other than Total having a value of Double-Blind Treatment Arm that is a merged field over the treatment group names.
- If possible, include 100% frequencies in the table shell, so that it is clear what the denominator is for percentage calculations.
- All listing outputs should be sorted (preferably by Subject Number) and will not reference double-blind treatment.
- Do not use superscripts and subscripts.
- Exponentiation will be expressed using a double asterisk, i.e., mm³ will be written as mm**3.

Author: [REDACTED]

Version Number:

7

Version Date:

07Dec2023

Template No.: CS_TP_BS016 Revision 6

Reference: CS_WI_BS005

Effective Date: 02Dec2019

- The width of the entire output should match the linesize.

Univariate Statistics:

- Statistics should be presented in the same order across tables (i.e., n, Mean, SD, Median, Minimum, Maximum).
- Table statistics should line up under the N part of the (N=XXX) in the table header. All decimal points should line up. If the minimum and maximum are output on one line as Minimum, Maximum then the comma should line up with the decimal point.
- If the original data has N decimal places, then the summary statistics should have the following decimal places:

Minimum and maximum: N

Mean and median: N + 1

SD or SE: $N + 2$

Frequencies and percentages (n and %):

- Percent values should be reported inside parentheses, with one space between the count and the left parenthesis of the percentage. Parentheses should be justified to accept a maximum of 100 as a value and padded with blank space if the percent is less than 100. An example is given below:

77 (100.0%)
50 (64.9%)
0 (0.0%)

- Percentages will be reported to no decimal places, except percents <100% but >99.5% will be presented as ‘>99%’ (e.g., 99.6% is presented as >99%); and percents < 0.5% will be presented as ‘<1%’ (e.g., 0.4% is presented as <1%).

Author:

Version Number:

7

Version Date:

07Dec2023

Template No.: CS TP BS016 Revision 6

Reference: CS WI BS005

Effective Date: 02Dec2019

Rounding will be applied after the <1% and >99% rule, noting that due to the small number of subjects this rule is only expected to be applicable for summaries of total number of administered doses by dose level.

e.g., (<1%)
(6.8%)
(>99%)

- Where counts are zero, no percentage will be displayed.

Spacing:

- There must be a minimum of 1 blank space between columns (preferably 2).

Denominators:

- If a different count other than the population count is used for a denominator (within the table) to calculate percentages, there should be a row in the table that identifies that number “n”.
- Alternatively, a footnote should be included in each table with percentages to indicate the denominator for percentages.

Missing values

- A “0” should be used to indicate a zero frequency.
- A blank will be used to indicate missing data in a subject listing.

8. FOOTNOTE INFORMATION

Footers should be defined as follows:

- A continuous line of underscores ('_') will follow the body of the table or listing prior to any footnotes at the bottom of the page.
- Table footnotes should be defined using compute statements in the proc report and

Author: [REDACTED] Version Number: 7
[REDACTED] Version Date: 07Dec2023

Template No.: CS_TP_BS016 Revision 6 Reference: CS_WI_BS005

Effective Date: 02Dec2019

should appear directly after the body of the table.

- The program path (starting with sponsor) and name should appear as footnote 1 at the bottom of the page and be left aligned, while the date/time stamp should appear right aligned on the same line.
- Footnotes should be left-aligned.
- Footnotes should be in sentence case.
- Only “typewriter” symbols are permitted – e.g., “*”, “\$”, “#”, “@”, “&” and “+”.
- The choice of footnote symbols should be consistent. E.g., if you have the footnote “# indicates last observation carried forward” for one table, the same symbol and footnote should indicate LOCF for all tables.
- If text wraps across more than one line (for a note), the first letter for all lines of text after the first one will be indented to align beneath the first letter of the text in the first line.

Ordering of footnotes should be as follows:

- 1.) Symbols
- 2.) Abbreviations and definitions
- 3.) Formulae
- 4.) Specific notes

- Common notes from table to table should appear in the same order.
- The symbols should appear in the same order as what they are defined in the table or listing, from left to right.

9. PROGRAMMING INSTRUCTION

Programming instructions must appear in blue font at the end of each table or listing shell.

Author: [REDACTED]

Version Number:

7

Version Date:

07Dec2023

Template No.: CS_TP_BS016 Revision 6

Reference: CS_WI_BS005

Effective Date: 02Dec2019

Programming instructions, where necessary, should follow the table or listing shells in blue font, beginning with the words “Programming Note” followed by a colon. These include notes on the output, reminders of how to handle missing values, repeat shells for similar tables etc.

DATES & TIMES

Depending on data available, dates and times will take the form yyyy-mm-ddThh:mm:ss.

SPELLING FORMAT

English US.

PRESENTATION OF TREATMENT GROUPS

For tables, treatment groups will be represented as follows and in the given order, noting that “Double-Blind Treatment Arm” will be displayed above the individual treatment columns:

- Placebo
- Solanezumab
- Gantenerumab
- Total

PRESENTATION OF VISITS

For outputs, OLE visits will be represented as follows and in that order (Note: refer to protocol for full list of OLE visits), noting that listings will display visits (including unscheduled visit) in date order:

Long Name (default)	Short Name
Baseline (OLE Visit 1)	BL (V1)
Week 4 (OLE Visit 2)	W4 (V2)
Week 8 (OLE Visit 3)	W8 (V3)
...	...
Week 48/52 (OLE Visit 14) *Note: due to a protocol amendment, assessments for year 1 occurring at either week 48 or week 52 will be displayed with the format above	W52 (V14)
...	...
Week 156 (Visit 40)	W156 (V40)
Early Termination	ET
Safety MRI 1 (120 mg)	OSM1
...	...
Safety MRI 11 (stable dose 5 MRI)	OSM11

Summaries and/or models including external and/or double-blind data may display timepoints based on the anticipated duration from treatment start or observational period start, such as Month 6 or Year 1, rather than using visit identifiers.

Author: [REDACTED]

Version Number:

7

Version Date:

07Dec2023

Template No.: CS_TP_BS016 Revision 6

Reference: CS_WI_BS005

Effective Date: 02Dec2019

APPENDIX 2. PARTIAL DATE CONVENTIONS

Missing dates will not be imputed. Note that conventions below will not be applied to items which are on CRF pages to capture ongoing events/medications from the double-blind period, as all such records will be considered as starting prior to OLE.

ALGORITHM FOR TREATMENT EMERGENCE OF ADVERSE EVENTS:

START DATE	STOP DATE	ACTION
Known	Known/Partial / Missing	
If start date < OLE study med start date, then not TEAE
 
If start date > study med start date, then TEAE
 
If start date = study med start date with AE start time present and < med start time, then not TEAE
 
If start date = study med start date with AE start time present and \geq med start time, then TEAE
 
If start date = study med start date with AE start time missing and AE noted as starting prior to OLE treatment, then not TEAE
 
If start date = study med start date with AE start time missing and AE noted as not starting prior to OLE treatment, then TEAE

Author: [REDACTED]

Version Number:

7

Version Date:

07Dec2023

Template No.: CS_TP_BS016 Revision 6

Reference: CS_WI_BS005

Effective Date: 02Dec2019

START DATE	STOP DATE	ACTION
Partial, but known components show that it cannot be on or after study med start date	Known/Partial / Missing	Not TEAE
Partial, could be on or after study OLE med start date OR Missing	Known	If stop date < OLE study med start date, then not TEAE If stop date \geq OLE study med start date, then TEAE
	Partial, could be on or after OLE study med start date OR Missing	Assumed TEAE

Author: [REDACTED]

Version Number:

7

Version Date:

07Dec2023

Template No.: CS_TP_BS016 Revision 6

Reference: CS_WI_BS005

Effective Date: 02Dec2019

ALGORITHM FOR PRIOR / CONCOMITANT MEDICATIONS:

START DATE	STOP DATE	ACTION
Known	Known	If start date < OLE study med start date, assign as prior If start date \geq OLE study med start date, assign as concomitant
Partial, could be on or after OLE study med start date OR Missing	Known	If stop date < OLE study med start date, assign as prior If stop date \geq study med start date, assign as concomitant
	Partial, could be on or after OLE study med start date OR Missing	Assign as concomitant

Author: [REDACTED]

Version Number:

7

Version Date:

07Dec2023

Template No.: CS_TP_BS016 Revision 6

Reference: CS_WI_BS005

Effective Date: 02Dec2019

